Primary Objective	
 • To evaluate patient preference of deferasirox FCT or deferasirox DT in patient with transfusion –dependent thalassemia or non-transfusion – dependent thalassemia as measured by preference questionnaire at Week 48
Secondary Objectives	
 • To evaluate patient’s palatability, GI symptom and satisfaction of deferasirox FCT or deferasirox DT or previous iron chelation based on Patient Reported Outcomes (PRO) • To evaluate patient preference of deferasirox FCT or deferasirox DT or previous iron chelation • To evaluate the reason behind preference for deferasirox FCT versus deferasirox DT

	
 • To evaluate the effect of deferasirox FCT compared with deferasirox DT on patient compliance using pill count • To evaluate the overall safety of deferasirox FCT compared with deferasirox DT • To evaluate efficacy of deferasirox (both formulations DT and FCT) in decreasing serum ferritin levels
Study design	
This is a an open-label, multicenter, single arm, phase II study aimed at collecting data on preference for iron chelation therapy in patients with transfusion-dependent thalassemia (TDT) or non-transfusion-dependent thalassemia (NTDT) throughout a 48 week treatment period.
 
The study is divided into 2 phases:
 
 - Core Phase: 
 • Screening period (visit number 1): which last up to 4 weeks to determine the patient eligibility, followed by, • Period 1: from Baseline visit Day 1 to Week 24: 
 • TDT patients: Deferasirox DT starting at 20 mg/Kg/day to maximum dose: 40 mg/Kg/day • NTDT patients: Deferasirox DT starting at 10 mg/Kg/day to maximum dose: 20 mg/Kg/day • Period 2: from Week 25 to Week 48: 
 • TDT patients: Deferasirox FCT starting at 14 mg/Kg/day to maximum dose: 28 mg/Kg/day • NTDT patients: Deferasirox FCT starting at 7 mg/Kg/day to maximum dose: 14 mg/Kg/day - Extension Phase: 
 • Deferasirox FCT: from Week 49 until Study Evaluation Completion (SEC - visit number 777) or until at least one of the End of Study criterion is met, whichever comes first: 
 • TDT patients: Deferasirox FCT starting at 14 mg/Kg/day to maximum dose: 28 mg/Kg/day • NTDT patients: Deferasirox FCT starting at 7 mg/Kg/day to maximum dose: 14 mg/Kg/day.

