2.3 Rationale for dose and regimen selection

Deferasirox is available in three dosing strengths: 125, 250 and 500 mg for dispersible tablets and 90, 180 and 360 mg for film-coated tablets.

For each patient, the dose is calculated by the physician based on the patient's weight, and then rounded up or down to the nearest tablet configuration, which can result in a variance between the calculated and actual dose of up to 15%. This dosing paradigm is consistent with how deferasirox DT (Exjade[®]) has been developed with regard to safety and efficacy.

All Deferasirox naïve patient or chelation naïve patients or patients who have been treated by other chelators such as Deferiprone (DFP) / Deferoxamine (DFO) or Combination (DFO + DFP) for at least 6 months continuously, at the study entry will use a starting dose of:

- Deferasirox DT of 20 mg/kg/day in transfusion-dependent thalassemia (TDT)
- Deferasirox DT of 10 mg/kg/day in non-transfusion-dependent thalassemia (NTDT),

The equivalent FCT starting dose is:

- Deferasirox FCT of 14 mg/kg/day in transfusion-dependent thalassemia (TDT)
- Deferasirox FCT of 7 mg/kg/day in non-transfusion-dependent thalassemia (NTDT).

For patients with difficulties in swallowing Deferasirox FCT, it is allowed to crush the film-coated tablets. It should be administered by sprinkling the full dose on soft food like yogurt or apple sauce (apple puree). For further instructions, refer to the [Appendix 14](#).

Dose adjustments are permitted as follows:

- Patients receiving the DT formulation: \pm 5-10 mg/kg/day; maximum daily dose: 40 mg/kg/day for TDT patients; 20 mg/kg/day for NTDT patients
- Patients receiving the FCT formulation: \pm 3.5-7 mg/kg/day; maximum daily dose: 28 mg/kg/day for TDT patients; 14 mg/kg/day for NTDT patients.

For ICT naïve patients at study entry the dose can be adjusted after 4 weeks of study treatment and for ICT pre-treated patients, the dose should be adjusted if necessary every 3 months based on serum ferritin levels

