6.1.1 Dosing regimen

Having completed the screening period (including the 5-day wash-out period for patients previously treated with Deferiprone/DFP or Deferoxamine/DFO), eligible patients will start the core phase and be switched on the Day 1 visit to deferasirox DT for 24 weeks followed by deferasirox FCT for 24 weeks duration. Upon completion of Week 48 (Core Phase), the patient can still be treated with deferasirox FCT for a maximum of another 48 weeks or until one of the end of study criteria defined is met, whichever comes first.

The starting dose on Baseline Day 1 would be as following:

- Deferasirox DT of 20 mg/kg/day in transfusion-dependent thalassemia (TDT)
- Deferasirox DT of 10 mg/kg/day in non- transfusion-dependent thalassemia (NTDT),

Table 6-1 Equivalent FCT starting dose at Week 25

Equivalent dose to be used	
Deferasirox DT (mg/kg/day)	Deferasirox FCT (mg/kg/day)
5	3.5
10	7
15	10.5
20	14
25	17.5
30	21

Equivalent dose to be used	
Deferasirox DT (mg/kg/day)	Deferasirox FCT (mg/kg/day)
35	24.5
40	28

All iron chelation pre-treated patients who had received treatment with deferoxamine (DFO) and deferiprone (DFP) will be initiated on deferasirox DT. The dose of deferiprone will be determined by their serum ferritin and the dose of deferoxamine by using the equivalent deferasirox DT dose (see [Appendix 14.2](#)).

Dose adjustment for better treatment effects, based on serum ferritin levels and investigator's judgment, will be allowed for ICT naïve patients after 4 weeks of study treatment and for ICT pre-treated patients every 3 months. The dose adjustments will be performed in steps of 5-10 mg/kg/day for deferasirox DT or in steps of 3.5-7 mg/kg/day for deferasirox FCT.

For each patient the daily dose is calculated by the physician based on the patient's actual body weight, and then rounded up or down to the nearest whole tablet according to the available strengths of deferasirox tablets (125 mg, 250 mg and 500 mg for the DT and 90 mg, 180 mg and 360 mg for the FCT, see [Appendix 14.1](#)).

The investigator should instruct the patient (or legal patient's representative in the case of pediatric patients) to take the study drug as prescribed. All doses planned and prescribed to the patient and all dose changes including reasons for change during the study must be recorded in the eCRF.

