Dose adjustments based on safety are allowed at any time point in the study and will be in increments of 5-10 mg/kg/day for deferasirox DT or 3.5-7 mg/kg/day for deferasirox FCT. Dose adjustments based on efficacy are permitted. For ICT naïve patients at study entry dose adjustments are allowed after 4 weeks of study treatment based on serum ferritin levels and investigator's judgement. For ICT pre-treated patients, the dose of deferasirox should be adjusted if necessary every 3 months based on the trends in serum ferritin and investigator's judgement. For more details please refer to [Table 6.2](#) – Dose of study drug based on serum ferritin level.

Table 6-2 Dose and treatment schedule

Study treatments	Pharmaceutical form and route of administration	Starting Dose* (weeks 1-4)	Dose adjustment (after week 4)	Max dose	Frequency and/or Regimen
Deferasirox DT – TDT patients	Dispersible tablets, p.o.	20 mg/kg/day	+ 5 - 10 mg/kg/day	40 mg/kg/day	Once daily
Deferasirox DT – NTD patients	Dispersible tablets, p.o.	10 mg/kg/day	+ 5 - 10 mg/kg/day	20 mg/kg/day	Once daily
Deferasirox FCT – TDT patients	Film-coated tablets, p.o.	14mg/kg/day	+ 3.5 - 7 mg/kg/day	28 mg/kg/day	Once daily
Deferasirox FCT – NTD patients	Film-coated tablets, p.o.	7 mg/kg/day	+ 3.5 - 7 mg/kg/day	14 mg/kg/day	Once daily

*Iron chelation naïve patients. All iron chelation pre-treated patients see [Section 6.1.1](#) and [Appendix 14.2](#) for guidance.

Table 6-3 Daily dose of study drug based on serum ferritin level

Dose Regimen of Drug for TDT patients	Serum ferritin level
20 mg/Kg Deferasirox DT 14 mg/Kg Deferasirox FCT	1000-1500 ng/ml
30 mg/Kg Deferasirox DT 21 mg/Kg Deferasirox FCT	>1500-2000 ng/ml
40 mg/Kg Deferasirox DT 28 mg/Kg Deferasirox FCT	>2000 ng/ml
Dose Regimen of Drug for NTD patients	Serum ferritin level
5 mg/Kg Deferasirox DT 3.5 mg/Kg Deferasirox FCT	300-799 ng/ml
10 mg/Kg Deferasirox DT	800-2000 ng/ml

Dose Regimen of Drug for TDT patients	Serum ferritin level
7 mg/Kg Deferasirox FCT	
20 mg/Kg Deferasirox DT 14 mg/Kg Deferasirox FCT	>2000 – 4000 ng/ml
30mg/Kg Deferasirox DT 21mg/Kg Deferasirox FCT	>4000ng/mL

Serum ferritin level will be measured monthly to evaluate the study drug response

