6.2.1.3 Changes in Serum Ferritin

Serum ferritin should be monitored monthly during the study as stated in the Visit Evaluation Schedule [Table 7-1](#) and [Table 7-2](#).

For ICT pre-treated patients, the dose of deferasirox DT should be adjusted if necessary every 3 months based on the trends in serum ferritin and investigator's judgement. [Table 6.2](#) provides additional guidance on suggested doses.

Dose adjustments should be made in steps of 5-10 mg/kg/day for deferasirox DT and of 3.5-7 mg/kg/day for deferasirox FCT and are to be tailored to the individual patient's response and therapeutic goals (maintenance or reduction of iron burden).

For TDT patients not adequately controlled with:

- Deferasirox DT doses of 30 mg/kg/day, doses of up to 40 mg/kg/day may be considered. Doses above 40 mg/kg/day are not permitted.
- Deferasirox FCT doses of 21 mg/kg/day, doses of up to 28 mg/kg/day may be considered. Doses above 28 mg/kg/day are not permitted.

For NTDT patients not adequately controlled with:

- Deferasirox DT doses of 15 mg/kg/day, doses of up to 20 mg/kg/day may be considered. Doses above 20 mg/kg/day are not permitted.
- Deferasirox FCT doses of 10.5 mg/kg/day, doses of up to 14 mg/kg/day may be considered. Doses above 14 mg/kg/day are not permitted.

In patients whose serum ferritin level has reached the target (usually between 500 and 1000 ng/mL for TDT patients or between 300-800 ng/mL for NTDT patients), dose reductions in steps of 5-10 mg/kg/day for deferasirox DT and of 3.5-7 mg/kg/day for deferasirox FCT should be considered to maintain serum ferritin levels within the target range.

If serum ferritin falls below 500 ng/mL for TDT patients and 300 ng/mL for NTDT patients, an interruption of study treatment should be considered until serum ferritin rises above 500 ng/mL or 300 ng/mL respectively.

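### The NTDT dose ceiling of 20/14 mg/kg conflicts with 30/21 mg/kg in Tables 6-3 and 14-17, three DT rows have wrong tablet counts, and Tables 14-7 and 14-13 skip whole dose steps

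*Protocol*

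**What the plan says.** **NTDT ceiling.** The protocol summary states "NTDT patients: Deferasirox DT starting at 10 mg/Kg/day to maximum dose: 20 mg/Kg/day". Section 2.3 repeats it: "maximum daily dose: 40 mg/kg/day for TDT patients; 20 mg/kg/day for NTDT patients". Table 6-2 has the same maxima (20 mg/kg DT, 14 mg/kg FCT). Section 6.2.1.3 is categorical for NTDT patients on DT: "Doses above 20 mg/kg/day are not permitted". It sets the matching FCT limit at 14 mg/kg. Against this, the NTDT part of Tables 6-3 and 14-17 gives, for ferritin above 4000 ng/mL, "30 mg/Kg Deferasirox DT 21 mg/Kg Deferasirox FCT".

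**NTDT start after deferiprone.** Section 2.3 includes patients coming from other chelators and gives "Deferasirox DT of 10 mg/kg/day in non-transfusion-dependent thalassemia (NTDT"). Section 6.1.1 opens with the same fixed dose ("The starting dose on Baseline Day 1 would be as following"). It then says of pre-treated patients "The dose of deferiprone will be determined by their serum ferritin". Section 7.1.2 and the equivalence guidance in Appendix 14.1 also base the DT dose after deferiprone on ferritin.

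**PPS rules.** SAP 5.5 excludes from the PPS any patient whose dose does not comply with Table 6-3 (S03) or whose maximum dose does not comply with Table 6-2 (S15 for DT, S16 for FCT).

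**Dosing tables.** Section 6.1.1 and Appendix 14.1 require the dose closest to mg/kg times weight that the tablet strengths allow. Section 2.3 expects rounding to move the dose by at most 15%.

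**The concern.** Sites prescribe and dispense from these tables, for children from age 2, and Section 8.6 provides no data monitoring committee. Two instructions for the same NTDT patient differ by half, and one exceeds a limit stated as absolute. In three rows, a pharmacist who follows the tablet columns dispenses a dose other than the one printed beside them. In two tables, a small difference in body weight moves a child from clear under-dosing to a dose above the maximum.

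The statistical stakes are narrower. A patient dosed as one part of the protocol directs can be dropped from the PPS for breaching another part. Dose errors that differ between the formulations also change exposure at the Week 25 switch, and so enter the DT-versus-FCT dose, ferritin and safety summaries for those children.

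**Working it through.** **1. The plan's own examples reproduce.** Dose = mg/kg × weight, rounded to the nearest multiple of 125 mg (DT) or 90 mg (FCT). For the 46 kg patient in Appendix 14.1: 20 × 46 = 920, closest 875 mg DT; 14 × 46 = 644, closest 630 mg FCT. Both match.

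**2. NTDT ceiling.** 30/20 = 1.5 and 21/14 = 1.5, so the table dose is 50% above the cap in both formulations. At ferritin above 4000 ng/mL:
- 20/14 mg/kg keeps to Table 6-2 but not Table 6-3: S03, out of the PPS.
- 30/21 mg/kg keeps to Table 6-3 but not Table 6-2: S15 or S16, out of the PPS.

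**3. Tablet counts.** The tablets were summed in all 165 DT rows (Tables 14-1 to 14-8) and all 187 FCT rows (Tables 14-9 to 14-16). Every FCT row adds up. Three DT rows do not:

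| Row | Stated | Printed tablets give | Error | mg/kg delivered |
|---|---|---|---|---|
| Table 14-5 (25 mg/kg), 27.6–32.5 kg | 750 mg | 2×250 + 500 = 1000 mg | +33% | 30.8–36.2 |
| Table 14-6 (30 mg/kg), 39.7–43.8 kg | 1250 mg | 250 + 500 = 750 mg | −40% | 17.1–18.9 |
| Table 14-8 (40 mg/kg), 23.5–26.6 kg | 1000 mg | 1×500 = 500 mg | −50% | 18.8–21.3 |

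Table 14-8 at 107.9–110.9 kg prints 4370 mg beside tablets that give 4375 mg. That is a label slip only.

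**4. Closest dose, Table 14-7 (35 mg/kg DT).** The table goes from 500 mg (14.0–19.9 kg) to 875 mg (20.0–26.5 kg), omitting 625 and 750 mg.
- At 19.9 kg: 35 × 19.9 = 696.5 mg, closest 750. Printed 500 mg is 25.1 mg/kg, −28%.
- At 20.0 kg: 35 × 20.0 = 700 mg, closest 750. Printed 875 mg is 43.75 mg/kg, +25%. Since 875/40 = 21.875, the 40 mg/kg maximum is exceeded up to 21.8 kg.

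**5. Closest dose, Table 14-13 (17.5 mg/kg FCT).** The table gives 180 mg up to 17.9 kg and then 360 mg, omitting 270 mg. At 17.9 kg: 17.5 × 17.9 = 313 mg, closest 270 (15.1 mg/kg, −14%). Printed 180 mg is 10.1 mg/kg, −43%.

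**6. Correct cut points.** The change from dose d to the next step is at (d + half a step)/(mg/kg).
- Table 14-7: 437.5/35 = 12.5; 562.5/35 = 16.1; 687.5/35 = 19.6; 812.5/35 = 23.2 kg.
- Table 14-13: 225/17.5 = 12.9; 315/17.5 = 18.0 kg.
- Table 14-5: 312.5/25 = 12.5; 437.5/25 = 17.5 kg.

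**7. Week 25 switch.** Section 1.2.2 equates 500 mg DT with 360 mg FCT by AUC, a ratio of 0.72. Mismatches were counted on a 0.1 kg grid.
- From 25 mg/kg DT as printed: at 14.0–16.9 kg, 375 × 0.72 = 270 mg but 180 is given (−33%); at 17.0–17.9 kg, 500 × 0.72 = 360 mg but 180 is given (−50%). Between 10.0 and 22.5 kg, 40 of 126 weights mismatch. Re-cutting Table 14-13 alone leaves 21, including +50% at 12.9–13.9 kg (250 mg DT to 270 mg FCT). Re-cutting Tables 14-13 and 14-5 together leaves 8.
- From 35 mg/kg DT, 10.0–23.0 kg: 91 of 131 weights mismatch as printed, 10 after the Table 14-7 re-cut.

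**The case against.** **The ferritin table is advisory.** Section 6.2.1.3 says its dose table "provides additional guidance on suggested doses" and leaves room for judgement, so a site could stay at 20/14 mg/kg. That is a fair reading of the protocol, but S03 carries no such exception. The amendment rationale cites NTDT doses of up to 30 mg/kg as effective, so the cap may be the part left unrevised. That bears on which figure to keep, not on whether the two agree.

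**Table 14-18 is only a conversion.** It maps deferoxamine 50–80 mg/kg to 25–40 mg/kg DT without an NTDT limit, but its wording is permissive and the cap still applies. This stands. It needs a note and is not a separate contradiction.

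**Reach is limited.** Tables 14-7, 14-13 and 14-5 serve 35 and 25 mg/kg DT (or its FCT equivalent). Table 6-3 does not name those doses; they arise only through 5 mg/kg steps or deferoxamine conversion. This stands too. By contrast, the faulty rows of Tables 14-6 and 14-8 serve 30 and 40 mg/kg, which Table 6-3 does name for transfusion-dependent (TDT) patients.

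**Stronger readings that the documents do not support.** A reader might infer:
- That a deferiprone-treated NTDT patient started at 30 mg/kg also breaches S01. The Table 6-2 footnote confines its starting doses to chelation-naive patients.
- That starting such a patient at 10 or 20 mg/kg breaches S08. S08 covers only patients doing well on their earlier chelator, which is hard to claim at ferritin above 4000 ng/mL.
- That S01 and S03 collide for naive TDT patients with high ferritin. This needs Table 6-3 to be a Day 1 rule, whereas Section 6.1.1 introduces it through dose adjustment, allowed in naive patients only after four weeks.
- That every low-weight row off the closest dose should be corrected singly. Some such edits do harm. Cutting Table 14-16 to 360 mg at 14.1–14.4 kg turns an exact switch (625 × 0.72 = 450 mg) into −20%. Cutting Table 14-14 to 180 mg at 10.5–10.7 kg turns another (375 × 0.72 = 270 mg) into −33%.

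**Conclusion.** Wrong as written, on three counts:
- The NTDT dose at ferritin above 4000 ng/mL is both directed and forbidden, with a 50% gap. On a literal reading of SAP 5.5, neither dose keeps the patient in the PPS.
- Three DT rows deliver +33%, −40% and −50% against their stated dose.
- Tables 14-7 and 14-13 miss the closest dose by skipping steps, with errors of −28%, +25% and −43% at the weights shown, against an expected 15%.

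The switch figures rest on the 500:360 mg equivalence in Section 1.2.2. The documents do not say how many patients fall in these groups. A reader might infer that the main result is at risk. It is not directly affected, because the primary test uses the full analysis set and the PPS analysis is supportive. The case for correction is dosing safety first, then the PPS and the between-formulation summaries.

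**What to change.** 1. **NTDT.** State one ceiling in the summary, Section 2.3, Table 6-2, Section 6.2.1.3, Table 6-3 and Table 14-17; the clinical team chooses the figure. Note that it also limits the Table 14-18 conversion. State one starting-dose rule for deferiprone-pretreated NTDT patients.
2. **SAP 5.5.** Apply S03 only from the first permitted adjustment and up to the ceiling. Judge S15 and S16 against that single ceiling.
3. **Tablet counts (125/250/500 mg).** Table 14-5, 27.6–32.5 kg: 0/1/1. Table 14-6, 39.7–43.8 kg: 0/1/2. Table 14-8, 23.5–26.6 kg: 0/0/2.
4. **Weight bands.**
   - Table 14-7: 375 mg to 12.5 kg, 500 mg 12.6–16.0, 625 mg 16.1–19.6, 750 mg 19.7–23.2, 875 mg 23.3–26.5.
   - Tables 14-13 and 14-5 together. Table 14-13: 180 mg to 12.8 kg, 270 mg 12.9–17.9. Table 14-5: 250 mg to 12.5 kg, 375 mg 12.6–17.4, 500 mg 17.5–22.5.
5. **Remaining rows below about 23 kg.** Re-check by program as DT/FCT pairs, against the closest dose, the maximum and the 500:360 mg switch ratio together.

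Cost: a protocol amendment with IRB/IEC approval (Section 12.1) and a SAP wording change. It changes the dose of some children already enrolled; Amendment 1 records 132 patients in the study at its date. No extra patients or procedures are needed.

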6.1.2 Ancillary treatments

Not applicable

6.1.3 Rescue medication

Not applicable

6.1.4 Treatment duration

The planned treatment duration of the core phase is 48 weeks and the planned treatment period for the extension phase is another 48 weeks.

The total duration of the study is approximately 104 weeks (including the Screening, Treatment, Study Evaluation Completion and Safety Follow-up visits).

6.2 Dose modifications

6.2.1 Dose modification and dose delay

For patients who are unable to tolerate the protocol-specified dosing schedule, dose reductions are permitted in order to keep the patient on study drug. These changes must be recorded on the dosage administration record in the eCRF.

For all cases where a dose adjustment is considered necessary but is not covered in the following sections, the investigator will send a written request to Novartis. The request must justify the dose change and provide all the supportive clinical and laboratory information for complete evaluation by Novartis. Any dose adjustment for reasons not included in this section needs to be authorized by Novartis. A written reply will be promptly sent back to the investigator by Novartis.

6.2.1.1 Change in patient's weight

The dose of study medication will be adapted using the Dosing Table (provided in Appendix 14.1) during the study in case the change (increase or decrease) in body weight exceeds 10% of the body weight compared to Visit 2 or the last dose adjustment due to a change in the patient's body weight.

6.2.1.2 Elevations in serum creatinine

Serum creatinine should be monitored during the study as stated in the [Table 7-1](#) and [Table 7-2](#).

In case of a single clinically relevant increase in serum creatinine, the assessment will be repeated at the next visit, or as clinically indicated.

Deferasirox dose reduction by 10 mg/kg/day for the DT formulation and by 7 mg/kg/day for the FCT formulation should be performed if there is a rise in serum creatinine by 33% above baseline value resulting in a serum creatinine above the ULN on two consecutive visits (a minimum of 7 days apart).

If after a dose reduction, a progressive increase in serum creatinine beyond the ULN is observed, a treatment interruption is recommended.

After a treatment interruption, if serum creatinine falls below the age appropriate upper limit of normal range on two consecutive visits, it is recommended to resume therapy at 50% of the last dose, and after 1 month, if the serum creatinine increase does not recur, study medication can be returned to 100% of the last dose (including body weight adjustment if required).

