6.2.1.4 Changes in urine protein/creatinine ratio

Proteinuria should be monitored during the study as stated in [Table 7-1](#) and [Table 7-2](#).

In case of a single increase of the urinary protein/creatinine ratio the assessment should be repeated at the next visit.

Deferasirox dose reduction by 50% should be performed if the urinary protein/creatinine ratio increases to > 0.5 mg/mg in two consecutive second-void urine samples (a minimum of 48h apart), if all other causes of proteinuria have been excluded.

Deferasirox must be temporarily interrupted if the urinary protein/creatinine ratio increases to > 1.0 mg/mg in two consecutive second-void urine samples (a minimum of 48h apart).

Should proteinuria persist, study treatment may be discontinued if the investigator believes it is in the best interest of the patient. Novartis may be contacted by the investigator to discuss dosing options if the investigator so desires.

Dose adjustment will be based on local laboratory results.

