| S11          | The dose adjustment in deferasirox DT not performed in increments of 5-10 mg/kg/day  | INCLUDE IN EVERYTHING | 0             |
| S12          | The dose adjustment in deferasirox FCT not performed in increments of 3.5-7 mg/kg/day  | INCLUDE IN EVERYTHING | 0             |
| S13          | Deferasirox dose was not temporarily interrupted despite urinary protein/creatinine ratio increases to > 1.0 (mg/mg) in two consecutive second-void urine samples (a minimum of 48h apart)               | INCLUDE IN EVERYTHING | 0             |
| S14          | Deferasirox dose was not temporarily interrupted even though the skin rash persists for > 1 week or becomes more severe  | INCLUDE IN EVERYTHING | 0             |
| S15          | Maximum dose of deferasirox DT is not compliant with Protocol table 6-2.   | EXCLUDE FROM PPS      | 4             |
| S16          | Maximum dose of deferasirox FCT is not compliant with Protocol table 6-2.  | EXCLUDE FROM PPS      | 4             |
| S17          | Dose adjustment of deferasirox DT is not compliant with Protocol table 6-2.  | EXCLUDE FROM PPS      | 4             |
| S18          | Dose adjustment of deferasirox FCT is not compliant with Protocol table 6-2.   | EXCLUDE FROM PPS      | 4             |
| S19          | Patient received incorrect dose due to dispensing error.   | Include in Everything | 0             |
| S20          | Cautious re-initiation of Deferasirox treatment at a lower dose was not done following Study medication interruption due to Increased liver enzyme levels (ALT/AST).                                     | Include in Everything | 0             |

| Deviation ID | Description of Deviation  | Exclusion in Analyses | Severity code |
|--------------|---|-----------------------|---------------|
| S21          | Deferasirox dose reduction by 10 mg/kg/day for the DT formulation and by 7 mg/kg/day for the FCT formulation was not performed following a rise in serum creatinine by 33% above baseline value resulting in a serum creatinine above the ULN on two consecutive visits (a minimum of 7 days apart) | Include in Everything | 0             |
| S22          | Resuming study medication dose is not done according to protocol following treatment interruption for abnormal Serum Creatinine.  | Include in Everything | 0             |

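### The fixed creatinine-triggered dose reduction equals the whole NTDT starting dose and exceeds the lowest dose level, so it is a full stop at one and impossible at the other

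*Protocol*

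**What the plan says.** Protocol 6.2.1.2 applies when serum creatinine is 33% above baseline and above the upper limit of normal on two consecutive visits at least 7 days apart. The instruction is "Deferasirox dose reduction by 10 mg/kg/day for the DT formulation and by 7 mg/kg/day for the FCT formulation should be performed". It is the same for transfusion-dependent (TDT) and NTDT patients. Two further steps follow. If creatinine keeps rising after the reduction, an interruption is recommended. After an interruption, once creatinine has recovered, "it is recommended to resume therapy at 50% of the last dose", with a return to the full last dose a month later if the rise does not recur.

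The doses on which this acts are set elsewhere:

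- Protocol 6.1.1 gives the starting dose "Deferasirox DT of 10 mg/kg/day in non- transfusion-dependent thalassemia (NTDT"), and Protocol 2.3 gives the equivalent "Deferasirox FCT of 7 mg/kg/day in non-transfusion-dependent thalassemia (NTDT"). Table 6-2 repeats both.
- Table 6-3 assigns "5 mg/Kg Deferasirox DT 3.5 mg/Kg Deferasirox FCT" to NTDT patients with serum ferritin of 300-799 ng/ml.
- Table 14-18 converts prior deferoxamine of 10 or 20 mg/kg/day to 5 or 10 mg/kg/day DT (3.5 or 7 FCT), and does not limit this to NTDT.

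Protocol 6.1.1 also has a general sentence: "Dose adjustments based on safety are allowed at any time point in the study and will be in increments of 5-10 mg/kg/day" for DT, with 3.5-7 mg/kg/day for FCT. SAP 5.5, Table 1, item S21 lists as a deviation that "Deferasirox dose reduction by 10 mg/kg/day for the DT formulation and by 7 mg/kg/day for the FCT formulation was not performed" after the creatinine trigger. Its code is 0, so the patient stays in every analysis set.

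**The concern.** An absolute subtraction has a different meaning at each dose level. At the TDT starting dose it halves the dose. At the NTDT starting dose nothing is left, and at the lowest level the step is larger than the dose. Protocol 6.2.1 says that reductions are allowed so that patients who cannot tolerate the schedule can stay on study drug. At the NTDT starting dose this reduction takes the patient off it.

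This is a renal safety instruction. At these levels a site that follows the text reaches a stop that the section does not call an interruption, or a step that it cannot make. The protocol does not say what to do in either case. A site that uses the wider increments in 6.1.1 instead is recorded under S21.

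**Working it through.** **Inputs.** Fixed step: 10 mg/kg/day DT, 7 mg/kg/day FCT (Protocol 6.2.1.2). Dose levels: Table 6-1, with the NTDT levels from Tables 6-2 and 6-3. General safety increment: 5-10 DT, 3.5-7 FCT (Protocol 6.1.1).

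**Consistency of the step.** Table 6-1 converts DT to FCT by a factor of 0.7, and 10 × 0.7 = 7. The two fixed steps agree with each other; the difficulty is their size relative to the lower doses.

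**Dose after the fixed step** = level − step. **Share removed** = step / level, which is the same for both formulations.

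| DT level | DT − 10 | FCT level | FCT − 7 | Share removed |
|---|---|---|---|---|
| 5 | −5 | 3.5 | −3.5 | 200% |
| 10 | 0 | 7 | 0 | 100% |
| 15 | 5 | 10.5 | 3.5 | 67% |
| 20 | 10 | 14 | 7 | 50% |
| 25 | 15 | 17.5 | 10.5 | 40% |
| 30 | 20 | 21 | 14 | 33% |
| 35 | 25 | 24.5 | 17.5 | 29% |
| 40 | 30 | 28 | 21 | 25% |

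A positive dose remains only from 15 DT / 10.5 FCT upwards.

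**Follow-on steps at 10 DT.** After the reduction the dose is 0, so the later interruption has nothing to interrupt. The restart depends on what the last dose means:

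- Dose after the reduction: 50% × 0 = 0.
- Last non-zero dose: 50% × 10 = 5 DT (FCT: 50% × 7 = 3.5).

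Section 6.2.1.2 does not choose between these.

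**Against the 6.1.1 increments.** The fixed step is the top of the 6.1.1 range, so the disagreement is about latitude.

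- From 10 DT the range allows 10 − 5 = 5 to 10 − 10 = 0. From 7 FCT it allows 7 − 3.5 = 3.5 to 0.
- From 5 DT even the smallest step gives 5 − 5 = 0. From 3.5 FCT it gives 3.5 − 3.5 = 0.

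**Against S21.** At 10 DT, a move to 5 is a change of 5. It satisfies 6.1.1 but is not a reduction of 10, so S21 records a deviation. At 5 DT, even a full stop is a reduction of only 5. Read literally, no action avoids S21.

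**How the low levels are reached.** NTDT entry requires ferritin of at least 800 ng/ml (Protocol 5.2), so the 300-799 band in Table 6-3 is not an entry level. It applies once ferritin falls, and 6.2.1.3 asks investigators to consider step-downs when the NTDT target is reached. Table 14-18 is a second route, open at entry to patients on low-dose deferoxamine. The 10 DT level is the NTDT starting dose itself.

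**The case against.** The best defence has four parts.

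- **At 10 DT / 7 FCT the rule can be carried out.** The answer is exactly zero, and a site can stop the drug. Protocol 10.3.1 and SAP 2.4.1 count interim zero-dose days as interruptions for exposure, and the dose record holds the planned dose, reason and dates. This stands. A reader might infer that the rule is unworkable at the starting dose, or that the summaries could not represent such a stop; the documents support neither.
- **The last dose can be read as the last non-zero dose.** A return to 100% of it makes sense only on that reading, and SAP 2.4.1 records the final daily dose as the last non-zero one. The restart then works at 10 / 7. This is a sensible reading, but 6.2.1.2 does not state it, so it remains to be defined. The stronger inference, that the follow-on steps have no dose to act on, does not hold.
- **Other routes exist.** The 6.1.1 increments give a smaller step at 10 / 7, and 6.2.1 has a written-request route to the sponsor. But if 6.1.1 governs, S21 contradicts it, and at 5 / 3.5 its smallest step is still zero. The request route is for adjustments that the sections do not cover. Creatinine has its own section, so its use here is at best arguable.
- **The consequences are limited.** S21 applies only after the compound trigger and carries code 0. No effect on the preference endpoint follows.

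A reader might also see a clash between the increments in 6.1.1 and the 50% rules, such as "Deferasirox dose reduction by 50% should be performed if the urinary protein/creatinine ratio increases". A specific rule that departs from a general one is ordinary drafting, and Appendix 14.1 rounds to the closest available dose. That argument is not relied on here.

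**Conclusion.** The contradiction is real and exact. The fixed step is 100% of the NTDT starting dose and 200% of the lowest level. At the first it turns a reduction into a stop, which the section's own sequence does not provide for. At the second it cannot be performed. No other passage removes the conflict: giving priority to 6.2.1.2 yields zero or a negative dose, and giving priority to 6.1.1 conflicts with S21 and still yields zero at 5 / 3.5.

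The conclusion rests on reading 6.2.1.2 as applying to all patients, since it contains no exception. It does not rest on any event rate. The documents give neither the number of NTDT patients nor the frequency of the creatinine trigger, so the number affected cannot be stated. The analysis sets and the primary analysis are not touched through S21. The case for acting is that a stated safety rule fails when it is followed, and that reconciling it is cheap.

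**What to change.** Reconcile Protocol 6.2.1.2 with the safety-increment sentence in 6.1.1, Tables 6-2, 6-3 and 14-18, and SAP S21. After reconciliation:

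- the creatinine rule should have an outcome that can be performed and recorded at every permitted DT and FCT level;
- the text should say whether the 6.1.1 increments or the fixed step govern after the creatinine trigger;
- the last dose in the restart rule should be defined;
- S21 should refer to the reconciled rule, so that following the protocol is not recorded as a deviation.

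The sponsor's clinicians decide the content. No dose or clinical rule is proposed here. The cost is a short protocol amendment and one SAP line, with no extra visits or tests.
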